2.5 Analysis of the primary objective

2.5.1 Primary endpoint

The primary efficacy variable is the proportion of patients who achieve an ASAS 20 at Week 16. The analysis of the efficacy variable will be based on the FAS.

The ASAS response measures consist of the following assessment domains ([Sieper, 2009](#)):

Main ASAS domains:

1. Patient’s global assessment of disease activity measured on a VAS scale
2. Patient’s assessment of back pain, represented by either total or nocturnal pain scores, both measured on a VAS scale. For ASAS response analyses, the total back pain will be used.
3. Function represented by BASFI average of 10 questions regarding ability to perform specific tasks as measured by VAS scale

4. Inflammation represented by mean duration and severity of morning stiffness, represented by the average of the last 2 questions on the 6-question BASDAI as measured by VAS scale

Additional assessment domains:

5. Spinal mobility represented by the BASMI lateral spinal flexion assessment
6. C-reactive protein (acute phase reactant)

The ASAS Response Criteria (ASAS 20) is defined as an improvement of $\geq 20\%$ and ≥ 1 unit on a scale of 10 in at least three of the four main domains and no worsening of $\geq 20\%$ and ≥ 1 unit on a scale of 10 in the remaining domain.

The ASAS20 response will be evaluated in subgroups based on previous use of TNF-alpha inhibitors, hsCRP value (≤ 10 mg/L, > 10 mg/L, and ≤ 5 mg/L, > 5 mg/L) at baseline, age (< 65 yr, ≥ 65 yr), gender, weight (< 70 kg, $70 - 90$ kg, > 90 kg) at baseline.

2.5.2 Statistical hypothesis, model, and method of analysis

A frequency table with the number and percentage of patients achieving an ASAS 20 at Week 16 will be presented. Because of the small number of patients in this study, the efficacy results will be presented in a descriptive manner. Neither statistical model nor statistical hypothesis is defined.

2.5.3 Handling of missing values/censoring/discontinuations

Missing data for ASAS 20 up to Week 52 will be handled as follows:

1. Patients who drop out of the trial for any reason will be considered non-responders from the time they drop out
2. Patients who do not have the required data to compute response (e.g. ASAS components) at baseline and at the specific time point will be classified as non-responders.

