### **5.5.6 Rescue medication**

Rescue medication is defined as any new therapeutic intervention or a significant change to ongoing therapy made because a patient is experiencing either no benefit from participation in the trial or worsening/exacerbation of their disease. Rescue medication must not be used before completion of Week 16 assessments. Although no patient will be restricted from receiving necessary rescue medications for lack of benefit or worsening of disease, if rescue with prohibited biologics (as described in [Section 5.5.8](#)) occurs, patients will be discontinued from the study. Efficacy will be assessed in detail at every study visit, and patients who are deemed not to be benefiting from the study treatment based on safety and efficacy assessments (see [Section 5.5.9](#)) or for any reason on their own accord will be free to discontinue participation in the study at any time. Changes in NSAID concomitant therapy are permitted as per investigator's clinical judgment after all Week 16 assessments are completed. Please see [Section 5.5.7](#), [Section 5.5.8](#) and [Section 5.5.9](#) for further details.

Any use of rescue medication must be recorded in the Prior/Concomitant medications eCRF page.

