2.3 Patient disposition, demographics and other baseline characteristics

2.3.1 Patient disposition

The number of patients who entered the screening period will be presented. In addition, the reasons for screen failures will be provided.

The number and percentage of patients in the safety set who completed treatment periods, and Post-treatment follow-up, and who discontinued the study prematurely (including the reason for discontinuation) will be presented.

For each protocol deviation (PD), the number and percentage of patients for whom the PD applies will be tabulated for entire period (i.e., all PDs will be presented.) in the safety set.

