2.4 Treatments (study treatment, rescue medication, concomitant therapies, compliance)

2.4.1 Study treatment / compliance

The analysis of study treatment data will be based on the safety set. The number of injections will be summarized. The duration of exposure to study treatment will also be summarized. In addition, the number and percentage of patients with cumulative exposure levels (e.g., any exposure, \geq 1 week, \geq 2 weeks, \geq 3 weeks, \geq 4 weeks, \geq 8 weeks, etc.) will be presented.

In general, duration of exposure is defined as the time from first dose of study treatment to the end of treatment period. The end of treatment period will be defined as the last dose plus 84 days or last visit (including Week F60 in the Post-treatment follow-up period), whichever occurs earlier, i.e., for patients who discontinued or have their last visit earlier than last dose plus 84 days, the end of study treatment exposure will be the date of the last study visit.

Duration of exposure (days) = (last visit date or last dose date + 84 days whichever comes earlier) – first dose date + 1

Duration of exposure (years) = duration of exposure (days) / 365.25

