2.4.2 Prior and concomitant therapies

Prior and concomitant medications will be summarized in separate tables based on the safety set. Prior medications are defined as treatments taken and stopped prior to first dose of study treatment. Any medication given at least once between the day of first dose of study treatment and within 84 days after last dose will be a concomitant medication, including those which were started pre-baseline and continued into the treatment periods.

Medications will be presented in alphabetical order, by Anatomical Therapeutic Classification (ATC) codes and grouped by anatomical main group. Tables will show the overall number and percentage of patients receiving at least one treatment of a particular ATC code and at least one treatment in a particular anatomical main group.

Prior surgeries and procedures are defined as surgeries and procedures done prior to first dose of study treatment. Any surgeries and procedures done between the day of first dose of study

treatment and within 84 days after last dose will be concomitant surgeries and procedures, including those which were started pre-baseline and continued into the period where study treatment is administered.

Significant prior and concomitant non-drug therapies and procedures will be summarized by primary system organ class and MedDRA preferred term on the safety set.

The number and percentage of patients receiving prior and concomitant ankylosing spondylitis therapy (disease-specific therapy) will be presented by category for medication preferred term on the safety set. The category is “Topical glucocorticoids”, “Systemic glucocorticoids”, “Nonsteroidal anti-inflammatory drugs”, “Tumour necrosis factor alpha inhibitor”, and “Other ankylosing spondylitis medication”. Glucocorticoids in the eCRF page will be divided into two; Topical one and Systemic one based on whether the Route (CMROUTE in SDTM) is Topical or not. The category for NSAIDs will be specified based on whether the data is from the NSAIDs CRF page or not.

At a minimum, methotrexate, sulfasalazine and systemic corticosteroid intake at baseline (Day 1) will be presented based on the amount taken per time unit, e.g. mg/day. Since different steroids have different strengths the following multiplication factors will be used to convert a dose in mg into a prednisone equivalent dose in mg:

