2.5.4 Supportive analyses

For binary efficacy variables, the percentage will be calculated based on the number of patients with an assessment at the analysis visits in the FAS (observed case analysis).

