2.7.3 Handling of missing values/censoring/discontinuations

These handlings for binary efficacy variables up to Week 52 will be the same as described in 2.5.3. For binary efficacy variables, the observed case analysis (the percentage calculated based on the number of patients with an assessment at the analysis visits in the FAS) is also performed as the supportive analysis.

Missing values for continuous efficacy variables will not be imputed. Summary statistics will be presented based on all data available at the analysis visits.

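### Should a patient given non-biologic rescue before Week 16 who stays in the study be counted as an ASAS20 non-responder, at least in a supplementary analysis?

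*SAP*

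**What the plan says.** The primary variable is the proportion of the full analysis set with an ASAS20 response at Week 16 (Protocol 9.4.1, SAP 2.5.1). SAP 2.5.3 repeats the two non-response rules of Protocol 9.4.3. The first is dropout: "Patients who drop out of the trial for any reason will be considered non-responders from the time they drop out". The second covers patients whose data are insufficient to compute response. SAP 2.7.3 carries the rules over to the other binary endpoints: "These handlings for binary efficacy variables up to Week 52 will be the same as described in 2.5.3". The one supportive analysis, in SAP 2.5.4, is the observed-case version, restricted to patients assessed at the visit. None of these sections mentions rescue.

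On rescue itself, Protocol 5.5.6 says "Rescue medication must not be used before completion of Week 16 assessments", and Protocol 3.1 and SAP 1.1 agree. The next sentence of 5.5.6 adds that "no patient will be restricted from receiving necessary rescue medications for lack of benefit or worsening of disease", and it ties removal from the study only to rescue with prohibited biologics.

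On reporting, the heading of SAP 2.4 names rescue medication, but 2.4.1 and 2.4.2 contain no rescue table. Concomitant medication is defined as "Any medication given at least once between the day of first dose of study treatment and within 84 days after last dose", with a separate table of ankylosing spondylitis therapy by drug category. For each protocol deviation, SAP 2.3.1 says "the number and percentage of patients for whom the PD applies will be tabulated for entire period".

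**The concern.** Rescue is given because a patient is not benefiting or is getting worse. If such a patient then meets ASAS20 at Week 16, part of the improvement may belong to the rescue drug. The study is single-arm and open-label, is meant to support registration, and all four main ASAS domains are reported by the patient. Compared with counting rescue as failure, scoring on observed values can only leave the rate unchanged or raise it.

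The supportive analysis does not help. It scores the same patient the same way and removes patients without an assessment from the denominator, so it cannot fall below the primary rate. The medication and deviation tables span the whole study and are not linked to Week 16 response. On this view a reader would never see the less favourable figure. With 30 patients, one or two could move a confidence limit that the sample size section describes as comfortably above the historical control.

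**Working it through.** **Who would be affected.** Reading the passages together, a patient changes status only if all of these hold:

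1. Rescue is given before the Week 16 assessments, although Protocol 3.1 and 5.5.6 and SAP 1.1 bar it. Table 5-1 separately bars unstable NSAID doses, systemic corticosteroids above its limit and intra-articular steroids until Week 16, unstable methotrexate or sulfasalazine until Week 52, and other DMARDs.
2. The rescue is not a prohibited biologic. If it is, the patient leaves the study under 5.5.6 and is a non-responder by the dropout rule.
3. The patient stays in the study. Protocol 5.5.9 tells the investigator to stop treatment when symptoms fail to improve or worsen, and sends patients who discontinue to end-of-treatment and final follow-up visits. The glossary allows treatment to stop without study withdrawal, so this step narrows the group but does not empty it.
4. All ASAS components are available. Otherwise the missing-data rule applies.
5. The observed values meet ASAS20.

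**Inputs.** n = 30 and an assumed rate of 60%, that is 18/30, with a stated lower 95% limit of about 42.5% and a control upper limit of 38.7% (Protocol 9.7, SAP Section 3). The interval method is the continuity-corrected score formula of SAP 5.4.1. The number of early-rescued responders, k, is not given in the documents. The values 0, 1 and 2 are assumptions.

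**Reproducing the plan's figure.** Wald: 0.60 − 1.96 × √(0.60 × 0.40 / 30) = 0.425, which matches 42.5%. The SAP 5.4.1 formula gives 40.8% for the same data.

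**Counting k rescued responders as failures.** Rate = (18 − k)/30, so each patient is worth 1/30 = 3.3 points.

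| k (assumed) | Rate | Lower limit, Wald | Lower limit, SAP 5.4.1 |
|---|---|---|---|
| 0 | 18/30 = 60.0% | 42.5% | 40.8% |
| 1 | 17/30 = 56.7% | 38.9% | 37.7% |
| 2 | 16/30 = 53.3% | 35.5% | 34.6% |

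For ASAS40 at about 40% (Protocol 1.1), one such patient moves 12/30 = 40.0% to 11/30 = 36.7%, and the SAP lower limit from 23.2% to 20.5%.

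**The observed-case analysis.** If two patients are assumed to have no Week 16 assessment, 18/28 = 64.3%. That rise comes from missing data, not rescue. With the denominator held at 28, one rescued responder counted as failure gives 17/28 = 60.7%, a step of 3.6 points. This is about the same as in the primary analysis.

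**What is already recorded.** Rescue use goes on the Prior/Concomitant medications eCRF (Protocol 5.5.6). Deviations are tabulated (SAP 2.3.1), and Protocol 11 requires significant ones to be reported in the study report. Protocol 5.5.7 asks patients to avoid NSAIDs and as-needed analgesics for at least 24 hours before a disease-activity visit, which limits short-term masking of symptoms.

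**The case for a change.** The best argument for a change is that the scoring, though determinate, is never stated for rescued patients and is never tested. The ban on early rescue is softened in the very next sentence of Protocol 5.5.6, so a rescued patient who remains in the study is foreseeable. The sample size section leans on the distance between the lower limit and 38.7%. One such patient takes the SAP-method limit below that value (37.7%), and two do so by either method. The remedy would be cheap: a sentence, one extra rate, a short listing and no new data.

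Part of this stands. The outputs shown do not link early rescue to response, and the direction of any effect is known. The two statements in 5.5.6 must also be reconciled by the sponsor. That is a matter of protocol wording, and either reading leaves the scoring rule as it is.

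The rest does not carry a change. The comparison with 38.7% is planning rationale, not a decision rule: Protocol 9.4.2 and SAP 2.5.2 define no hypothesis and present results descriptively. The extra rate is also less clean than it sounds. Neither document says what makes a change of therapy significant, as-needed analgesics are permitted throughout, and no rescue flag is described. Someone would have to classify records after the Week 24 interim analysis, which SAP 2.14 reports as done, in an open-label study where Week 16 responses are already known. A post hoc rate built that way would be weaker evidence than a plain account of any patients concerned.

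**Conclusion.** No change to the plan. The rule for the binary endpoints is the same in protocol and SAP, gives one answer for every patient, and follows a legitimate strategy of using the observed outcome whether or not rescue was taken. It produces no wrong number. If the protocol is followed, nobody is rescued before Week 16 and the effect is exactly zero. If it is breached, each rescued responder who stays in with complete data adds 3.3 points to the ASAS20 rate compared with counting rescue as failure. With about 30 patients, anyone who knows how many such patients there were can bound the effect at k/30. The deviation reporting and medication records already planned are where that count would be found. A listing of those patients with their ASAS20 status, or a statement that there were none, would be a helpful courtesy in the study report but does not need an amended analysis.

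This rests on two things: the counts of 0, 1 and 2 are assumptions because the documents give no rescue frequency, and the reading covers the public text, in which SAP 2.5.3, 2.5.4 and 2.7.3 are fully legible but some other parts are not shown.

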2.5.4 Supportive analyses

For binary efficacy variables, the percentage will be calculated based on the number of patients with an assessment at the analysis visits in the FAS (observed case analysis).

2.6 Analysis of the key secondary objective

2.6.1 Key secondary endpoint

Not applicable

2.6.2 Statistical hypothesis, model, and method of analysis

Not applicable

2.6.3 Handling of missing values/censoring/discontinuations

Not applicable

2.7 Analysis of secondary efficacy objective(s)

2.7.1 Secondary endpoints

ASAS 40 at Week 16

The ASAS 40 response is defined as an improvement of $\geq 40\%$ and ≥ 2 units on a scale of 10 in at least three of the four main domains and no worsening at all in the remaining domain.

Total BASDAI and BASDAI 50 at Week 16

The BASDAI consists of a 0 through 10 scale (1 being no problem and 10 being the worst problem), which is used to answer 6 questions pertaining to the 5 major symptoms of AS:

1. Fatigue
2. Spinal pain
3. Joint pain / swelling
4. Areas of localized tenderness (called enthesitis, or inflammation of tendons and ligaments)
5. Morning stiffness duration
6. Morning stiffness severity

To give each symptom equal weighting, the mean (average) of the two scores relating to morning stiffness (Q5 and Q6 above) is taken. The resulting 0 to 50 score is divided by 5 to give a final 0 – 10 BASDAI score (total BASDAI). Scores of 4 or greater suggest suboptimal control of disease, and patients with scores of 4 or greater are usually good candidates for either a change in their medical therapy or for enrollment in clinical trials evaluating new drug therapies directed at AS. BASDAI is a quick and simple index taking between 30 secs and 2 mins to complete.

At least 4 questions should be non-missing to calculate the BASDAI score. Otherwise, the BASDAI score will be regarded as missing ([Haywood 2002](#)). If both Q5 and Q6 are missing or one of Q1 to Q4 is missing the total sum should be divided by 4 instead of 5. If two of Q1 to Q4 is missing and both Q5 and Q6 are not missing the sum should be divided by 3.

The BASDAI50 is defined as a 50% improvement over the initial total BASDAI ([Braun, 2003](#); [Rudwaleit, 2004](#)).

hsCRP at Week 16

This assessment will be performed in order to identify the presence of inflammation, to determine its severity, and to monitor response to treatment.

ASAS 5/6 at Week 16

The ASAS 5/6 improvement criteria is an improvement of $\geq 20\%$ in at least five domains.

SF-36 PCS at Week 16

See Section 2.11 Patient-reported outcomes.

ASQoL at Week 16

See Section 2.11 Patient-reported outcomes.

ASAS partial remission at Week 16

The ASAS partial remission criteria is defined as a value not above 2 units in each of the domains 1 to 4 on a scale of 10.

Pharmacokinetics of secukinumab in Japanese patients

See Section 2.9 Pharmacokinetic endpoints.

2.7.2 Statistical hypothesis, model, and method of analysis

Given the small number of patients in this study, the efficacy results will be presented in a descriptive manner. Neither statistical model nor statistical hypothesis is defined.

ASAS 40 at Week 16

A frequency table with the number and percentage of patients achieving an ASAS 40 at Week 16 will be presented.

BASDAI 50 at Week 16

A frequency table with the number and percentage of patients achieving a BASDAI 50 at Week 16 will be presented.

hsCRP at Week 16

For the change in hsCRP at Week 16, since evidence from the literature would suggest that the data is not normally distributed ([Huffman, 2006](#)), summary statistics will be provided on the \log_e ratio of the treatment value vs. baseline value (calculated by dividing the post-baseline value by the baseline value and then applying the \log_e transformation) to normalize the distribution of hsCRP. Summary statistics for the observed values and the change from baseline at Week 16 will be presented.

ASAS 5/6 at Week 16

A frequency table with the number and percentage of patients achieving an ASAS 5/6 at Week 16 will be presented.

Total BASDAI at Week 16

Summary statistics for the observed values and the change from baseline at Week 16 will be presented.

SF-36 PCS at Week 16

See Section 2.11 Patient-reported outcomes.

ASQoL at Week 16

See Section 2.11 Patient-reported outcomes.

ASAS partial remission at Week 16

A frequency table with the number and percentage of patients achieving an ASAS partial remission at Week 16 will be presented.

Pharmacokinetics of secukinumab in Japanese patients

See Section 2.9 Pharmacokinetic endpoints.

2.7.3 Handling of missing values/censoring/discontinuations

These handlings for binary efficacy variables up to Week 52 will be the same as described in 2.5.3. For binary efficacy variables, the observed case analysis (the percentage calculated based on the number of patients with an assessment at the analysis visits in the FAS) is also performed as the supportive analysis.

Missing values for continuous efficacy variables will not be imputed. Summary statistics will be presented based on all data available at the analysis visits.

2.8 Safety analyses

Summaries will be performed for entire treatment period in the Safety set.

2.8.1 Adverse events (AEs)

Only treatment emergent adverse events are summarized. However all AEs are included in the listing with flags for treatment emergent. Non-treatment emergent adverse events may be summarized separately upon request.

Treatment emergent adverse events are defined as events started after the first dose of study medication or events present prior to the first dose of study medication but increased in severity after dosing based on preferred term and within last dose + 84 days.

The crude incidence of treatment emergent adverse events will be summarized by primary system organ class and preferred term. Confidence intervals for the crude rate will be derived as described in 5.4.4. In addition, exposure time-adjusted rates (incidence rate) including 95% confidence intervals will be provided for entire treatment period described below.

- Primary SOC level for AE
- Primary SOC and PT level for SAE

- Level 1 for risks and SMQ

AEs will be summarized by presenting the number and percentage of patients having any AE, having an AE in each primary system organ class and having each individual AE (preferred term). AEs reported will be presented in descending frequency according to its incidence in all patients starting from the most common event. Summaries (crude incidences only) will also be presented for AEs by severity and for study treatment related AEs. If a particular AE 'severity' is missing, this variable will be listed as missing and treated as missing in summaries. If a patient reported more than one adverse event with the same preferred term, the adverse event with the greatest severity will be presented. If a patient reported more than one adverse event within the same primary system organ class, the patient will be counted only once with the greatest severity at the system organ class level, where applicable.

Separate summaries will be presented for AEs possibly related to study treatment, death, serious adverse events (SAEs), SAEs possibly related to study treatment, AEs leading to discontinuation and AEs leading to temporary dose interruption.

Adverse events will also be reported separately by SMQ according to MedDRA, using a narrow search. The MedDRA version used for reporting the study will be described in a footnote.

In addition, crude incidence of AEs will be derived by 3 months intervals (only the first occurrence will be counted in case of multiple occurrences.)

For SAEs occurred during screening a listing will be prepared for all patients screened including screening failures.

MedDRA version used is the latest one at the analysis performed and will be specified in the subsequent SAP by clinical database lock as applicable.

Based upon the clinical information disclosure requirements of ClinicalTrials.gov and EudraCT, two required tables on treatment-emergent adverse events which are not serious adverse events with an incidence greater than 5% and on treatment-emergent serious adverse events and SAE suspected to be related to study treatment will be provided by system organ class and preferred term in the safety set population.

If for a same patient, several consecutive AEs (irrespective of study treatment causality, seriousness and severity) occurred with the same SOC and PT:

- a single occurrence will be counted if there is ≤ 1 day gap between the end date of the preceding AE and the start date of the consecutive AE

- more than one occurrence will be counted if there is > 1 day gap between the end date of the preceding AE and the start date of the consecutive AE

For occurrence, the presence of at least one SAE / SAE suspected to be related to study treatment / non SAE has to be checked in a block, e.g., among AEs in a ≤ 1 day gap block, if at least one SAE is occurring, then one occurrence is calculated for that SAE.

The number of deaths resulting from SAEs suspected to be related to study treatment and SAEs irrespective of study treatment relationship will be provided by SOC and PT.

